6.4.3 Handling Dropouts or Missing Data

6.4.3.1 Imputation of Missing Efficacy Data

The missing data handling rule for the study eye will be applied for the efficacy endpoints.

Missing data from subjects who discontinue the study before POD15 assessments without taking rescue medication:

For subjects who prematurely discontinue the study without taking rescue medication, the LOCF approach will be used to impute the missing data. The last observation will be the last assessment value after the first dose of study drug and up to two days following the last dose of study drug.

Missing data from subjects who discontinue the study before POD15 assessments and take rescue medication before POD15 assessments:

For both categorical and continuous secondary efficacy endpoints of ACC grade, ocular pain grade and ACF grade, subjects who take rescue medication before POD15 assessments and prematurely discontinue the study, the LOCF approach will be used to impute the missing data. The last observation will be the last assessment value after the first dose of study drug and prior to starting rescue medication.

Intermittent missing data:

The likelihood of having intermittent missing data is low. For subjects with intermittent missing data for efficacy endpoints, the LOCF approach will be applied to impute the missing data, i.e., using the data collected from the most recent prior visit after the first dose of study drug.

If no data can be carried forward (i.e., missing assessments at POD 4 visit or no available post-baseline assessments), missing data will be treated as missing for the continuous endpoints and will be considered as 'Non-responder' for the categorical endpoints.

6.4.3.2 Imputation of Partial Dates for Birthday, AEs, and Medications

The day of birth date will not be collected in order to protect subjects' privacy. To calculate the age from birth date, the day will be assigned as the 1st day of the birth month.

For analysis of AEs and medications (other than the study drug), a complete date should be established in order to determine treatment emergent AEs (TEAEs) or concomitant medications. The imputation rule of partial dates will be applied for missing components of partially-reported start and stop dates for AEs and for medication use.

Partial start dates of AE and medication will be imputed as follow:

- If only the month and year are reported and the month and year of the start date is not the same as the month and year of the date of first dose of study drug, then use the first day of the month.

- If only the month and year are reported and the month and year of start date is the same as the month and year of the date of the first dose of study drug, then use the date of first dose.
- If only the year is reported, and the year of the start date is not the same as the year of first dose of study drug, then use the January 1st as the start day and month.
- If only the year is reported, and the year of the start date is the same as the year of first dose of study drug, then use the date of first dose.
- If the start date is completely unknown and the stop date is partially known or not prior to the date of first dose of study drug, then use the date of first dose.
- If the imputed start date is after the known stop date, set the start date to be the same as the stop date.

Partial stop dates of AE and medication will be imputed as follow:

- If only the month and year are reported, then use the last day of the month
- If only the year is reported, then use December 31st of that year

If the unknown dates cannot be used to determine whether an AE is treatment emergent or a medication is concomitant, the AE will be considered as treatment emergent or the medication will be considered as concomitant.

In subject data listings, birthday, start and stop date of AEs or medications (other than study drug) will be displayed as reported (i.e., no imputed values will be displayed in data listings).

6.4.4 Handling of Dropouts Due to the COVID-19 Pandemic

The [protocol Appendix A](#) describes the Early Termination/Withdrawal procedures that may be implemented because of the COVID-19 pandemic. Subjects who discontinue the study due to COVID-19 will follow the imputation rules described in [Section 6.4.3.1](#) to impute the missing efficacy data.

6.4.5 Multicenter Studies

The randomization will be stratified by study site. No study sites will be pooled for analysis purposes, as the efficacy analyses will not be adjusted for study site differences. If there is a potential site issue identified, an exploratory analysis may be performed to adjust for 'study site' in the analysis of primary efficacy endpoints.

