10.3.2 Analysis of Efficacy

All efficacy analyses and summaries will be based on assessments in the study eye for each subject.

Subjects who are rescued at any time prior to Visit 5 (POD15) will be considered as treatment failures for the primary efficacy endpoints and the relevant secondary efficacy endpoints. For subjects who discontinue from the study prior to Visit 5 (POD15), the last observation carried forward (LOCF) approach will be used to impute missing data.

For continuous secondary efficacy endpoints, the LOCF approach will also be used to impute the data at visits after subjects are rescued.

The ACC count will be graded as shown below:

Grade	0	1	2	3	4
ACC Count	0 cell	1-5 cells	6-15 cells	16-30 cells	> 30 cells

10.3.2.1 Analyses of Primary Efficacy Endpoints:

The primary efficacy analyses to compare APP13007 against placebo will be conducted on the ITT population using the Pearson Chi-square statistic. Fixed sequence testing will be employed to maintain the 2-sided alpha = 0.05. The primary analyses will first test the difference between treatments in the proportion of subjects with ACC count = 0 (Grade = 0) at POD8 (Visit 4) maintained through POD15 (Visit 5). If the test is statistically significant at the 2-sided alpha = 0.05 level in favor of APP13007, the difference between treatments in the proportion of

subjects with Ocular Pain grade = 0 at POD4 (Visit 3) maintained through POD15 (Visit 5) will be tested at the two-sided alpha = 0.05 level.

To confirm the robustness of primary analysis results, sensitivity analyses, including using observed data from all subjects, will be performed. The detailed sensitivity analyses will be described in the SAP.

10.3.2.2 Analyses of Secondary Efficacy Endpoints:

Mean change-from-baseline in ACC Grade, ocular Pain Grade, ACF Grade and visual acuity at PODs 4, 8 and 15 will be analyzed using an analysis of covariance (ANCOVA). The ANCOVA model will include treatment as a fixed effect and baseline as a covariate. The rest of secondary efficacy endpoints will be analyzed using the same method described for the primary efficacy endpoints.

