10.1.2 Primary Analysis

The Pearson's Chi-square test will be used to test the null hypothesis that there is no difference between treatment groups for the primary efficacy endpoints:

1. The proportion of subjects with ACC count = 0 (ACC grade = 0) at POD8, maintained through POD15
2. The proportion of subjects with Ocular Pain grade = 0 at POD4, maintained through POD15

Since the treatment comparisons of the primary efficacy endpoints are in sequential order, the fixed-sequence hierarchical testing approach will be used to adjust for multiple comparisons. The primary analysis will first compare the proportion of subjects with ACC count = 0 (ACC grade = 0) at POD8, maintained through POD15, between APP13007 and placebo. If the test is statistically significant at the 2-sided $\alpha = 0.05$ level in favor of APP13007, the comparison of the

proportion of subjects with Ocular Pain grade = 0 at POD4, maintained through POD15, between APP13007 and placebo will be tested at the two-sided $\alpha = 0.05$ level.

Under the hierarchical testing scheme, once the two-sided p-value exceeds 0.05, the endpoint further down in the sequence will not be claimed for statistical significance.

The tabulated summary of the two endpoints will include the Responder (Response = Yes) and Non-responder (Response = No) for ACC count = 0 (ACC grade = 0) at POD8, maintained through POD15, or for Ocular Pain grade = 0 at POD4, maintained through POD15, and the 95% confidence interval (CI) for Responder. The treatment difference of the Responder rates with the associated 95% CI will be presented. The Response will be further categorized as:

Yes (Responder):

- Yes – Without imputed data
- Yes – With imputed data

No (Non-responder):

- No – With Rescue Medication Use
- No – Without Rescue Medication Use
- No – With imputed data

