10.1.3 Sensitivity Analyses

Sensitivity analyses will be performed to confirm the robustness of the primary efficacy analysis results:

1. Analysis of the primary endpoints will be performed using the PP population.
2. “Completed-Case” analysis of the primary endpoints will be performed using the subgroup of Completers based on the ITT population. Completers are defined as the subjects who complete the study and have the data for the ACC count and ocular pain grade assessments at all visits up to POD15.
3. “Observed-Case” analysis of the primary endpoints will be performed using the ITT population and the observed data for subjects who miss one of the assessments used to determine the primary endpoints without taking rescue medication. The subjects with missing data will be considered as treatment failures (Non-responders).
4. “Worst-Case in the Analysis Window” analysis of the primary endpoints will be performed using the ITT population and using the worst Response at PODs 4, 8 and 15 when multiple efficacy assessments fall within the same analysis window for each Analysis Visit.
5. If more than 5% of data are missing for determining the primary efficacy endpoints in any treatment group, a tipping point analysis will be performed when the statistical significance of a treatment difference between two groups has been claimed for each of the two primary

endpoints. Missing data for subjects who take a rescue medication will not be considered as 'missing' since the subjects will have been assigned as treatment failures (Non-responders).

The tipping point analysis of the primary endpoints will be performed using the ITT population to determine the number of subjects with imputed data in the placebo group whose response status has to be changed from Non-Responder to Responder in order to make the treatment difference between the two treatment groups no longer statistically significant.

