10.1.4 Additional Analysis

The primary efficacy endpoints will be analyzed using the data collected up to POD15. The rescued subjects will not be considered as treatment failures (Non-responders) for this analysis. All subjects' data collected up to POD15, including the data from subjects who take rescue medication, will be used to analyze the primary efficacy endpoints. Only observed data will be included to derive the primary efficacy endpoints. For the primary endpoint of ACC grade, subjects who miss one of POD 8 and POD15 assessments will be considered as treatment failures (Non-responders). For the primary endpoint of ocular pain grade, subjects who miss one of PODs 4, 8 and 15 assessments will be considered as treatment failures (Non-responders). The Pearson's Chi-square test will be used to test the treatment difference.

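### Randomization is stratified by site, but no committed efficacy analysis uses site: a minor, conservative loss of efficiency if sites differ

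*SAP*

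**What the plan says.** SAP 6.4.5 states "The randomization will be stratified by study site", and the next sentence reads "No study sites will be pooled for analysis purposes, as the efficacy analyses will not be adjusted for study site differences". It then leaves one door open: "If there is a potential site issue identified, an exploratory analysis may be performed to adjust for" site in the primary endpoints. It does not say what counts as a site issue, who decides, whether the decision comes before unmasking, or which method would be used.

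For both primary endpoints SAP 10.1.2 says that the Pearson "Chi-square test will be used to test the null hypothesis that there is no difference between treatment groups". Protocol 10.3.2.1 agrees: the analysis is "conducted on the ITT population using the Pearson Chi-square statistic". SAP 10.1.2 adds "The treatment difference of the Responder rates with the associated 95% CI will be presented", without naming the interval method.

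No other efficacy analysis commits to using site:
- SAP 10.1.3 opens with "Sensitivity analyses will be performed to confirm the robustness of the primary efficacy analysis results"; none of its five analyses includes site.
- In SAP 10.1.4 the Pearson "Chi-square test will be used to test the treatment difference".
- SAP 10.2.2.1 handles the categorical secondary endpoints like the primaries.
- The ANCOVA in SAP 10.2.2.2 contains treatment and baseline only.
- The rescue comparison in SAP 10.2.2.3 is a Pearson test.
- The subgroups in SAP 6.4.7 are age, race, gender and iris color.

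Site otherwise appears only in the disposition tables of SAP 7.1.

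**The concern.** Stratifying by site balances the arms within each site, so differences between sites largely cancel out of the treatment comparison. The unstratified variance does not reflect this. Under the null, with site response rates p_s and overall rate p, Pearson uses p(1 − p) per subject. With arms balanced within site, the variance that matters is the average of p_s(1 − p_s), which equals p(1 − p) − Var(p_s). If sites differ, Var(p_s) is positive, the standard error is too large, the test rejects less often than 5% under the null, and an unstratified interval for the difference is wider than the enrolled sites require.

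What is at stake is efficiency, not validity. A further gap is that the one site-adjusted analysis could be run or omitted, and its method chosen, after the results are known.

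**Working it through.** **Planning figures reproduced.** Inputs from SAP 4 and protocol 10.4: 26% against 12% for anterior chamber cell count zero (ACC), 57% against 38% for pain grade zero, two-sided 5%, 175 per arm, 185 randomized. With p the mean of the two rates,

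power = Φ{[Δ√n − 1.96·√(2p(1 − p))] / √(p₁(1 − p₁) + p₂(1 − p₂))}.

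- ACC, n = 175: (0.14 × 13.229 − 1.96 × 0.5548)/0.5459 = 1.40, power 91.9% (stated 92%).
- Pain, n = 175: (0.19 × 13.229 − 1.96 × 0.7062)/0.6933 = 1.63, power 94.8% (stated 95%).
- With 185 per arm the same formula gives 93.3% and 95.8%.

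**Simulation inputs.** The protocol synopsis gives about 30 sites and 370 subjects at 1:1. The documents give no block size, site sizes or between-site variance, so these are assumed: permuted blocks of 4 within site, unequal site sizes (gamma-multinomial), a common odds ratio, and normal site effects on the logit scale. Marginal rates are held at the planned values (null: 19% for ACC, 47.5% for pain). At the planned placebo rates, the middle 90% of sites would span:

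| Site SD | ACC | Pain |
|---|---|---|
| 0.5 | 5–22% | 21–58% |
| 1.0 | 2–33% | 10–74% |
| 1.5 | 1–44% | 4–86% |

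**Tests compared.** Pearson is Z = (difference in proportions)/√[p(1 − p)(1/n_T + 1/n_C)]. CMH is Σ(x_s − m_s n_Ts/n_s) / √Σ[m_s(n_s − m_s) n_Ts n_Cs / (n_s²(n_s − 1))], where x_s is active responders and m_s total responders at site s. Sites with fewer than 4 subjects were pooled for CMH. There were 100,000 trials per scenario (Monte Carlo SE on size about 0.07 point).

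Two-sided size (%), Pearson / CMH:

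| Site SD | ACC | Pain |
|---|---|---|
| 0 | 5.1 / 5.0 | 5.4 / 5.1 |
| 0.5 | 4.6 / 5.0 | 4.8 / 5.1 |
| 1.0 | 3.8 / 5.0 | 3.5 / 5.0 |
| 1.5 | 2.8 / 5.0 | 2.3 / 4.9 |

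Power (%), Pearson / CMH:

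| Site SD | ACC | Pain |
|---|---|---|
| 0 | 93.6 / 93.5 | 96.1 / 95.7 |
| 0.5 | 93.8 / 94.0 | 96.3 / 96.5 |
| 1.0 | 94.5 / 95.6 | 96.9 / 98.0 |
| 1.5 | 94.9 / 97.1 | 97.6 / 99.1 |

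At SD 1.0, CMH alone reaches p < 0.05 in 1.3% (ACC) and 1.1% (pain) of trials; Pearson alone does so in 0.1% and 0.04%.

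**Interval for the treatment difference.** The ratio of the unstratified to the Mantel-Haenszel (Sato) standard error at SD 0, 0.5, 1.0 and 1.5 is 0.997, 1.012, 1.056, 1.115 for ACC and 0.997, 1.023, 1.086, 1.164 for pain. For the difference across the enrolled sites, the unstratified interval covers 95.2–95.4%, 96.2–96.5% and 97.1–97.6% at SD 0.5, 1.0 and 1.5; Mantel-Haenszel covers 94.9–95.3%.

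**Robustness.** With 20 or 40 sites, or blocks of 8 (40,000 trials each), Pearson size at SD 1.0 is 3.5–4.0% and the power gain 1.0–1.2 points. A separate simulation with equal site sizes (12 or 13) and with sizes skewed from 2 to 50 shows the same pattern.

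**The case against.** The strongest reply is that this is an open and coherent choice. SAP 6.4.5 states the non-adjustment plainly, protocol and SAP name the same test, and the sample size was computed for that test. All of that stands, and it is why the point is not a validity error.

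The size of the loss also rests on an assumed site spread. Protocol 7.2.2.1 leaves examiners their usual technique but fixes light, magnification, angle and beam. Protocol 7.2.2.2 prescribes one pain scale, and the entry criteria are uniform. A spread as large as SD 1.0 is possible but not shown. This stands too, so the result is given as a range that includes no effect.

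Two technical objections are correct but small. With no site differences, Pearson for pain has size 5.4% rather than 5%; the exact calculation at 185 per arm and a rate of 47.5% also gives 5.4%. That is ordinary discreteness, unrelated to the stratification. Second, the Mantel-Haenszel interval is calibrated for the enrolled sites only. For a wider population of sites at SD 1.0, coverage of the unstratified and Mantel-Haenszel intervals is 93.9% and 92.6% for ACC, and 96.3% and 94.5% for pain. The plan should therefore say which sites the interval describes.

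Finally, replacing a protocol-named test may seem out of proportion to the gain. A fixed sensitivity analysis avoids that step. The objection does not answer the undefined trigger, or the absence of any committed check that uses the stratification factor.

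**Conclusion.** The concern holds as a minor point. The trial randomizes within site, yet no committed efficacy analysis uses site. If sites differ, the primary tests are conservative: about 1 point of power per endpoint is lost at a site SD of 1.0, about 1.5 to 2 points at 1.5, and almost nothing at 0.5 or below. An unstratified interval for the treatment difference is then about 6–9% wider than needed at SD 1.0 and 11–16% wider at SD 1.5, for the enrolled sites. The single-arm responder intervals are not part of this point.

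Site stratification does not inflate the type I error, the estimate is not biased, and with all 370 subjects in the ITT analysis Pearson exceeds 92% and 95% power in every scenario. The direction follows from the design. The size depends on the assumed site variance, site sizes and block size.

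**What to change.** **Preferred.** In SAP 6.4.5 and 10.1.2, make the site-stratified CMH test primary, with a Mantel-Haenszel risk difference and 95% CI. Name the variance method and state that the interval refers to the enrolled sites. Set any rule for pooling very small sites while masked, before database lock. The threshold is the sponsor's choice: pooling sites under 4 subjects, or not pooling at all, changes CMH power by at most 0.24 point. Keep Pearson as a sensitivity analysis.

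**If Pearson must stay primary.** Add the site-stratified CMH test and risk difference to SAP 10.1.3 as a fixed sensitivity analysis, and delete the conditional site-issue wording from 6.4.5.

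In either case, name the method for the CI of the treatment difference in SAP 10.1.2.

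**Cost.** A few lines of SAP text and code, with no new data or patients. Changing the primary test needs a protocol note; adding a sensitivity analysis does not. If sites turn out not to differ, making CMH primary costs at most about 0.5 point of power (30 sites: pain 96.1 to 95.7%; 40 sites unpooled: pain 96.0 to 95.5%, ACC 93.6 to 93.2%).

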6.4.6 Multiple Comparisons/Multiplicity

Since the comparisons of the primary efficacy endpoints will be performed in the pre-specified sequential order, the fixed-sequence hierarchical testing approach will be used to adjust for multiple comparisons. These endpoints will be tested in the sequence with the rule that once a

p-value exceeds 0.05, the endpoint further down in the sequence will not be claimed for statistical significance.

6.4.7 Subgroup Analyses

The primary efficacy endpoints will be evaluated for subgroups of interest, including:

- Age (< 65 or \geq 65 years)
- Race (White or Non-White)
- Gender
- Iris color (Blue, Brown or Other)

Subgroup summary will be performed using the ITT population for the primary efficacy endpoints only if the number of subjects in a subgroup is appropriate. No statistical comparisons will be conducted.

7. STUDY POPULATION CHARACTERISTICS

7.1 Subject Disposition

Summaries of the number of subjects screened, the number of screen failures, the number of subjects randomized and the number of subjects randomized in the Sub-study will be produced for all screened subjects.

All randomized subjects will be tabulated by treatment group and study site. Randomized subjects in the Sub-study will also be tabulated by treatment group and study site.

The number of subjects in each analysis population (ITT, PP and Safety) will be tabulated by treatment group for all randomized subjects. The number of subjects in the Safety population will be tabulated for subjects in the Sub-study.

The number and percentage of subjects who complete the study and who prematurely discontinue the study, along with the reason for withdrawal, will be tabulated by treatment group for the ITT population.

The number and percentage of subjects in the Sub-study who complete the Sub-study and who prematurely discontinue the Sub-study, along with the reason for withdrawal, will be tabulated by treatment group for the ITT population.

In addition, the numbers and percentages of subjects who discontinue the study drug before completing the 14-days of dosing and the reason for discontinuing the study drug will be tabulated by treatment group using the Safety population.

Disposition data for all screened subjects will be listed.

7.2 Protocol Deviations

Protocol deviations will be collected in the eCRF. The protocol deviation data will be reviewed for major protocol deviations by the clinical team prior to database lock and unmasking of the study treatment.

The subjects with major protocol deviations including the category of the major protocol deviations will be summarized by treatment group for the ITT population. The number and percentage of subjects excluded from the PP population and the reason for exclusion will be tabulated by treatment group for the ITT population.

The protocol deviation data will be listed. The data listing will include the type of deviation, the category of the deviation (major/minor), the status of being excluded from the PP population (yes/no) and reason for exclusion.

A data listing of subjects who do not meet the inclusion and exclusion criteria will be provided.

8. DEMOGRAPHICS AND BASELINE CHARACTERISTICS

8.1 Demographics and Baseline Characteristics

Demographic data, including age, age category (< 65 or \geq 65 years), gender, race, ethnicity, iris color, study eye (OD or OS) will be summarized by treatment group and overall. In addition, a summary of the demographic data for the subjects in the Sub-study will be presented.

Demographic and baseline characteristics data, including the data collected on the surgery day (Day 0), will be listed in data listings. Data of contact lens use will be listed for the subjects in the Sub-study.

